### **8.3 Secondary Objectives**

#### **8.3.1 Progression-free and Overall Survival**

Progression-free Survival (PFS) will be defined from date of allogeneic HCT to the date of disease progression or death. Patients who are still alive at last follow-up date without disease progression will be censored at that date. OS will be defined from date of allogeneic HCT to date of last known vital sign. Patients who are still alive at the last follow-up visit will be censored. A contemporary cohort of patients with ALL being transplanted in first complete remission will be identified prospectively. PFS and OS will be estimated using the Kaplan-Meier method and differences between the patients receiving blinatumomab and the contemporary cohort will be determined using the log-rank test. Patient outcomes in the contemporary cohort will be stratified by MRD status.

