## 1.0 Objectives

1.1 Primary: To assess the feasibility of blinatumomab post allogeneic hematopoietic cell transplantation (HCT) as consolidation therapy in patients with B-lineage acute lymphoblastic leukemia (ALL). Toxicities attributable to blinatumomab, acute GVHD, and secondary graft failure will be the parameters to define feasibility.

1.2 Secondary:

1.2.1 To evaluate the progression-free survival (PFS) rate at 1-year for patients with ALL compared to contemporary patient cohort.

1.2.2 To evaluate other efficacy endpoints such as overall survival (OS) and minimal residual disease (MRD) negativity rate in patients treated with blinatumomab for consolidation therapy.

1.2.3 To evaluate, non-relapse mortality (NRM) and chronic GVHD.

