overt hematologic relapse within a median of 3.8 months (4). Of note, among 32 patients with overt relapse following HCT, 41% did NOT have preceding MRD, suggesting that positive MRD post HCT essentially confirms eventual relapse, but negative MRD post HCT in a high-risk patient does not preclude relapse. Our findings corroborate similar published studies (5,6). Patients transplanted beyond second remission routinely have a significantly lower PFS and OS rates. In our study of 97 patients (CR1 51, CR2 29, others 17) treated with busulfan and clofarabine chemotherapy conditioning following a matched sibling (MSD) or matched unrelated donor (MUD) transplant, patients in CR1 had a significantly better disease free survival (DFS) compared with others (Figure 1). For patients in CR1, the 2-yr DFS rate was 61% with 9/51 patients relapsing at median 9 months, the 2-yr DFS rate was 40% for CR2, with 10/29 relapsing at median 3 months, and for patients with more advanced disease, the 2-yr DFS rate was 33% with 3/17 progressing at a median of 3 months. Our preliminary results with this regimen were similar (7). Data from the Center for International Blood and Marrow Transplant Research (CIBMTR) corroborate our findings. Between 1996 and 2001, in patients less than 20 years-old, OS ranges from 25% for patients transplanted beyond first remission to 50% for sibling transplants in first remission. Similarly, in adult patients, greater than 20 years-old, the best outcome is noted in sibling transplants done in first remission with OS of 60%, as compared to 35% if transplants are performed beyond CR1 (CIBMTR Registry).

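### PFS and OS are timed from transplant and tested against a CR1 cohort with no delayed entry or landmark, so the trial curves contain guaranteed event-free time

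*Combined protocol and SAP*

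**What the plan says.** Secondary objective 1.2.1 is a comparison: "To evaluate the progression-free survival (PFS) rate at 1-year for patients with ALL compared to contemporary patient cohort". Section 8.3.1 sets the clock for both endpoints at transplant: "Progression-free Survival (PFS) will be defined from date of allogeneic HCT to the date of disease progression or death", and "OS will be defined from date of allogeneic HCT to date of last known vital sign". The comparator is described in one sentence: "A contemporary cohort of patients with ALL being transplanted in first complete remission will be identified prospectively". The test is then stated: "differences between the patients receiving blinatumomab and the contemporary cohort will be determined using the log-rank test". The only refinement is "Patient outcomes in the contemporary cohort will be stratified by MRD status".

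Entry to the trial is governed elsewhere. Section 4.1 places enrolment between day 30 and day 100 after transplant, once counts and organ function have recovered. Section 4.2 excludes patients with more than 5% blasts. Section 5.3 puts the first cycle within 3 months of transplant. Table 3 allows consent up to 14 days before therapy.

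**The concern.** A patient can enter the trial group only by being alive and free of overt relapse at enrolment. Because the group tested is those who receive the drug, survival is guaranteed up to the first dose. Under 8.3.1 that waiting time counts as time at risk from day 0, although no death could occur in it.

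The cohort carries no such condition. Finding controls prospectively says how they are identified, not when they join the risk set. Stratifying by MRD status deals with prognosis, not entry time. A cohort patient who relapses or dies on day 40 is an event, whereas a would-be trial patient with the same course is never enrolled.

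This lifts the trial group's Kaplan-Meier curves whether or not blinatumomab works. It affects objective 1.2.1, the plan's only between-group efficacy comparison. The primary decision rests on the stopping rule and is untouched.

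**Working it through.** The plan gives no sample size, alpha, event count or power for this comparison, so there is no stated figure to reproduce.

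**Inputs from the protocol.** 30 trial patients (Table 5). Enrolment on day 30-100 (4.1). First cycle within 3 months, taken as day 91 (5.3). Event rate from section 2.1: "For patients in CR1, the 2-yr DFS rate was 61% with 9/51 patients relapsing at median 9 months".

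**Assumptions.** Hazard shape: constant (Weibull k = 1) or front-loaded (k = 0.7). First dose uniform from day 30. Cohort of 60 or 150. Follow-up of 12 or 24 months. Nominal 2.5% per side. No drug effect.

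**Step 1: apparent 1-year PFS.** With S(t) = 0.61^((t/730)^k), a patient first dosed on day e contributes S(365)/S(e) instead of S(365).

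| | k = 1 | k = 0.7 |
|---|---|---|
| True 1-year PFS, S(365) | 78.1% | 73.8% |
| S(30), S(91), S(100) | 98.0%, 94.0%, 93.5% | 94.8%, 89.1%, 88.4% |
| Apparent, first dose day 30 | 79.7% | 77.8% |
| Apparent, first dose day 91 | 83.1% | 82.8% |
| Apparent, first dose day 100 | 83.6% | 83.4% |

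For example, at k = 1 and day 91, 0.781/0.940 = 0.831. Averaged over uniform first doses to day 91 or day 100, the k = 1 value is 81.4% or 81.6%, a gap of 3.3 or 3.5 points. At k = 0.7 and first doses to day 100 the average is 80.7%, a gap of 6.9 points.

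**Step 2: early cohort events.** At k = 1, 1 - 0.940 = 6.0% of the cohort has had an event by day 91. In a cohort of 60 that is 0.060 × 60 = 3.6 patients.

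**Step 3: do the protocol's data settle the shape?** The median event time within 24 months solves S(t) = 1 - 0.39/2 = 0.805, so t = 24 × (ln 0.805/ln 0.61)^(1/k) = 24 × 0.439^(1/k). That is 10.5 months at k = 1 and 7.4 months at k = 0.7. The reported CR1 median of 9 months, for relapses only, lies between the two, so both shapes are carried forward.

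**Step 4: log-rank simulation at equal prognosis** (61% in both groups, 8,000 replicates per scenario). Share of runs falsely favouring blinatumomab:

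| Analysis | k = 1 | k = 0.7 |
|---|---|---|
| As planned, first dose to day 91 or 100 | 3.6-4.9% | 6.7-10.1% |
| As planned, all first doses by day 45-60 | 2.8-3.6% | 4.7-7.1% |
| Left truncation at first dose (both shapes) | 1.3-2.4% | 1.3-2.4% |
| Day-100 landmark in both groups (both shapes) | 1.0-2.3% | 1.0-2.3% |

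The Monte Carlo standard error at 4% is √(0.04 × 0.96/8000) ≈ 0.2 points. With 30 controls, the as-planned figures are 3.4-5.6% and 6.1-10.5%.

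**Step 5: higher-risk trial group** (first dose to day 91 or 100, still no drug effect):

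| Trial vs cohort 2-year DFS | For the drug, as planned | Against, as planned | Against, left-truncated |
|---|---|---|---|
| 50% vs 61% | 0.2-2.4% | 1.9-12.8% | 11.9-22.7% |
| 40% vs 61% | 0-0.4% | 7.9-44.9% | 31.0-60.7% |

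Here the results against the drug reflect case mix. Guaranteed time hides part of that difference.

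**The case against.** The strongest objection is that equal prognosis is unlikely. Section 4.1 selects patients beyond CR1, with induction failure, MRD or high-risk genetics, while the cohort is CR1. With that imbalance, false findings for blinatumomab are at or below nominal (Step 5), and left truncation alone makes findings against it more frequent. This stands, and it is why no net direction is claimed. It does not rescue the test: two uncontrolled biases of unknown size do not cancel reliably. Section 4.1 also does not require MRD-positive or high-risk-genetics patients to be beyond CR1, and for any in CR1 the offset is smaller.

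Several narrower points also stand:

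- **Case-mix figures depend on shape.** Section 2.1 gives CR2 relapse at a median of 3 months. Matching that needs k of about 0.45 in the trial group, treating relapse timing as event timing. At 40% vs 61%, results against the drug then become 5.6-22.2% as planned and 21.7-42.2% left-truncated, so the upper ends in Step 5 may be too high.
- **Truncation is not perfectly calibrated at n = 30.** At equal prognosis its unfavourable side ran at 2.6-4.4% against 2.5%. This is minor, but should be known.
- **The guarantee is certain only for OS.** Progression is undefined and MRD-positive patients may enter. If MRD counted as progression, PFS events could precede entry.
- **The anchor is soft.** The 61% comes from 51 patients in a series with 13 months' median follow-up.

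**Conclusion.** The concern holds. Followed as written, 8.3.1 gives a comparison that is biased by construction, and nothing else in the document supplies a landmark, an index day or delayed entry.

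The size is modest under constant hazard and material if events come early. For an average first dose, the inflation in 1-year PFS is about 3 to 7 points. The favourable-side error rises from 2.5% to roughly 4-10% when prognosis is equal and first doses extend to day 91 or 100. Those sizes rest on the assumed shape, dosing distribution, cohort size and alpha; the omission itself does not. The size for OS was not calculated.

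This should be fixed before analysis, but it is confined to secondary objectives. The CR1-only comparator is a separate and possibly larger problem.

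**What to change.** In 8.3.1, keep transplant as the time origin but enter each treated patient into the risk set at first dose, using left-truncated Kaplan-Meier estimates and a left-truncated log-rank test for PFS and OS. Begin the curves at a stated day with an adequate risk set. As a sensitivity analysis, apply one landmark to both groups, no earlier than the last permitted first dose; day 100 would suit first dosing within 3 months. Define progression, including whether MRD counts. State that left truncation does not correct the CR1 case-mix difference and that, used alone, it makes significant results against blinatumomab more frequent.

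Related edits:

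- **NRM (8.3.3):** use the same delayed entry, since the curve cannot contain deaths before entry.
- **Entry windows:** enrolment to day 100 (4.1) and a first cycle within 3 months (5.3) must be reconciled, because guaranteed time ends at first dose.
- **GVHD (8.2):** this is more a choice of what to estimate. Consider reporting onset or worsening after first dose, with earlier GVHD listed as a baseline characteristic. Report acute and chronic separately, given objective 1.2.3 ("To evaluate, non-relapse mortality (NRM) and chronic GVHD").

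**Cost.** The change needs only transplant, first-dose and event dates, and standard software. The result will look less favourable, because patients not yet dosed no longer count as at risk while early cohort events accrue. The early curve will be unstable. With 30 patients dosed uniformly on days 30-91 and ignoring events, 30 × (45 - 30)/61 ≈ 7 are at risk at day 45 and 30 × (60 - 30)/61 ≈ 15 at day 60. A day-100 landmark drops anyone with an event between first dose and day 100.

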## 4.0 Patient Eligibility

### 4.1 Inclusion Criteria:

1. Patients 1-70 years of age.
2. Patients with B-lineage ALL in a) hematologic complete remission (CR) beyond CR1 at time of transplant; b) primary induction failure defined as requiring more than one line of induction therapy; c) positive minimal residual disease defined by positive flow >0.01% before or after transplant; or d) high risk cytogenetic or molecular features consisting of Ph-like phenotype, detection of BCR-ABL transcript by PCR with a sensitivity of 1/10,000, or detection of the t(9;22) translocation in any metaphases by cytogenetics at time of transplant, or presence of the MLL gene before or after transplant.
3. Received an allogeneic HCT within the last 100 days. Enrollment within 30-100 days after transplant, and after adequate recovery of counts defined as ANC  $\geq 0.5 \times 10^9/L$  without daily use of myeloid growth factor and platelet  $> 20 \times 10^9/L$  without platelet transfusion within 1 week, and adequate organ function to receive blinatumomab defined as creatinine clearance greater than 30 ml/min (or greater than 60 ml/min/1.73), ALT/AST  $< 5 \times$  ULN and serum bilirubin  $< 3 \times$  ULN.
4. Performance status of 0, 1, or 2. Karnofsky (or Lansky for subjects < 16 years old) performance status  $\geq 50$ .

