### 4.2 Exclusion criteria:

1. Relapsed ALL defined as >5% malignant blasts in bone marrow or peripheral blood.
2. Active GVHD requiring systemic steroid therapy. Medications for GVHD prophylaxis are acceptable.
3. Systemic steroid therapy unless for physiologic replacement
4. Uncontrolled disease/infection as judged by the treating physician
5. Active ALL in the central nervous system (CNS), as defined by  $\geq 5$  leukocytes per  $\mu L$  with identifiable blast cells in the CSF (CNS 3 disease), and/or the presence of cranial-nerve palsies.
6. Pregnant or nursing women

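### PFS and OS from transplant are compared with a CR1 cohort by an unadjusted log-rank test, so case mix and delayed entry bias the result in opposite directions

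*Combined protocol and SAP*

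**What the plan says.** Objective 1.2.1 is 1-year PFS compared with a contemporary cohort. Section 8.3.1 sets out how:

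- Time origin: "Progression-free Survival (PFS) will be defined from date of allogeneic HCT to the date of disease progression or death". OS also starts at transplant.
- Comparator: "A contemporary cohort of patients with ALL being transplanted in first complete remission will be identified prospectively".
- Test: "differences between the patients receiving blinatumomab and the contemporary cohort will be determined using the log-rank test".
- The only stratification: "Patient outcomes in the contemporary cohort will be stratified by MRD status".

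Section 4.1 defines who is treated. The first disease route is "Patients with B-lineage ALL in a) hematologic complete remission (CR) beyond CR1 at time of transplant". The others are primary induction failure, "positive minimal residual disease defined by positive flow >0.01% before or after transplant", and high-risk cytogenetic or molecular features. Timing is "Enrollment within 30-100 days after transplant, and after adequate recovery of counts defined as ANC" and other recovery thresholds. Section 4.2 excludes "Relapsed ALL defined as >5% malignant blasts in bone marrow or peripheral blood" and active GVHD that needs systemic steroids.

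The plan states no matching, covariate adjustment, landmark or left truncation, and no eligibility rule for the cohort beyond ALL transplanted in CR1.

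**The concern.** The two groups differ in ways that affect PFS whether or not the drug works.

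**Case mix, against blinatumomab.** Section 2.1 defines the target population as MRD-positive and/or beyond CR1, and reports significantly better DFS for CR1 than for the rest. The comparator is nonetheless CR1. Stratifying the cohort's outcomes by MRD does not split the trial arm, and it does not deal with remission number, induction failure or genetics.

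**Delayed entry, in favour of blinatumomab.** The clock starts at transplant, but a trial patient must be alive, without overt relapse, with recovered counts and without steroid-requiring GVHD when enrolled at day 30-100. Time before entry is largely event-free by selection. (Section 8.3.1 does not define progression, so lesser progression before enrolment is not strictly excluded.) No such condition is stated for the cohort.

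At stake is the first-listed secondary objective: a formal p-value could be taken as evidence on efficacy when it partly reflects who was compared and from when.

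**Working it through.** The documents give no alpha, power, effect size or comparator number for this comparison, so there is no planned figure to reproduce. The checks below show direction and rough size.

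**1. Case mix.** Inputs (section 2.1): 2-year DFS 61% in CR1 (n=51) and 40% in CR2 (n=29). With a constant hazard, h = -ln(S)/2.

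- CR1: -ln(0.61)/2 = 0.247 per year, so 1-year DFS is 78.1%.
- CR2: -ln(0.40)/2 = 0.458 per year, so 1-year DFS is 63.2%.
- Hazard ratio: ln(0.40)/ln(0.61) = 1.85.

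Approximate interval: Var[log(-log S)] = (1-S)/(n S (ln S)^2), ignoring censoring before 24 months. This gives 0.0513 + 0.0616 = 0.1129, SE 0.336, and 95% CI 1.85 x exp(±1.96 x 0.336) = 0.96 to 3.6. The true interval is wider, because median follow-up was 13 months.

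**2. Delayed entry.** 1-year PFS given event-free at day d is S(1)/S(d), again with constant hazard and no drug effect.

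| | From transplant | Event-free at day 30 | Event-free at day 100 |
|---|---|---|---|
| CR1-like | 78.1% | 79.7% | 83.6% |
| CR2-like | 63.2% | 65.7% | 71.7% |

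Against a CR1 cohort at 78.1%, CR2-like patients entering at day 100 show a deficit of 78.1 - 71.7 = 6.4 points instead of 14.9. CR1-like patients entering at day 100 show a spurious gain of 83.6 - 78.1 = 5.5 points.

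A constant hazard probably understates early CR2 events. Section 2.1 has 10/29 CR2 patients relapsing at a median of 3 months, so about 5/29 = 17% had relapsed by month 3. The constant hazard allows only 1 - 0.40^(3/24) = 10.8% for all events. For CR1, the timing of events other than relapse is not given.

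**3. Log-rank test with no drug effect.** Assumptions: 30 trial patients (the maximum in Tables 5 and 6), 30-100 comparators, 12 months of follow-up, entry uniform on days 30-100, two-sided 5%. The early-hazard case triples the hazard in the first 100 days in both groups and keeps the 2-year rates.

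| Trial patients vs CR1 cohort | Error | Constant hazard | 3x early hazard |
|---|---|---|---|
| All CR2-like | false harm | about 11-19% | about 4-7% |
| All CR2-like | false benefit | under 1% | under 1% |
| All CR1-like | false benefit | about 4-6% | about 12-14% |

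With constant hazards and half the entrants CR2-like, false harm is 4-6%. With one third it is 2.9-3.5%, close to the nominal 2.5%. If the hazard ratio is moved to the ends of its interval (all CR2-like, constant hazard), false harm runs from about 1% to 64-87%.

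**4. Does correcting one bias suffice?** No.

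- Entry corrected, CR1 cohort kept (2-year follow-up): the no-effect hazard ratio moves from 1.38-1.77 to 1.86-2.11, because delayed entry no longer masks case mix.
- Risk-matched cohort, entry uncorrected (all CR2-like, 12 months): false benefit is 7-8% with a constant hazard and 16-18% if 3-month DFS is 80%.
- Both corrected, by left truncation: false benefit is about 2%.
- Both corrected, but entry at enrolment and only dosed patients counted: with an assumed 30-day gap to first dose, false benefit is about 3-4%, or 7-9% with the 3x early hazard.

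**The case against.** **The plan is silent on cohort selection, and silence is not exclusion.** This stands. The cohort is to be identified prospectively, but when after transplant and on what criteria is not said. A reader might infer that comparators will face none of the trial's entry conditions; the text supports only that none is stated. Lineage is a minor point too, since objective 1.2.1 also calls the trial's own patients simply patients with ALL.

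**A CR1 cohort is a demanding benchmark, so a win would mean something.** Partly right. A reader might infer that no log-rank result could be informative. That goes too far: if enrolment proves mainly CR2-like, a significant benefit would be conservative with respect to these two biases, and the mix will be known at analysis. But the plan gives no such rationale, and a null or unfavourable result would remain unreadable.

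**Some entrants will be in CR1.** True: the induction-failure, MRD and genetics routes can admit them. This weakens the case-mix bias and leaves delayed entry to dominate, so the sign depends on an enrolment mix that the plan does not give.

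**The percentages depend on assumed hazards.** This stands. Tripling the early hazard in both groups cuts false harm by more than half and more than doubles false benefit among CR1-like entrants.

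**It is a secondary comparison in a feasibility study.** Agreed; that limits the severity but does not make the planned test sound.

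**Conclusion.** The comparison is wrong as written. It puts high-risk patients who entered at day 30-100 against a cohort defined by CR1, counts both from transplant, and applies an unadjusted test. These facts come from the text and need no simulation. The two biases have opposite signs. Because neither the enrolled mix nor the early hazard is given, the net direction cannot be known in advance. A reader might infer from 61% versus 40% that the test is simply stacked against the drug; the documents do not support that, since CR1 patients can enter and delayed entry pulls the other way.

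The error rates are illustrations under the stated assumptions. They are not bounds, and they vary widely over the hazard ratio's interval. A null or unfavourable result could not be interpreted as a drug effect. A significant benefit could be called conservative on these two biases only if entrants prove mainly CR2-like. The primary feasibility rule is unaffected. The point should be fixed, but it does not threaten the main purpose of the trial.

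**What to change.** Amend section 8.3.1 as follows.

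1. **Cohort.** B-lineage ALL transplanted in the same period, not given blinatumomab, meeting the section 4.1 disease-risk criteria, and within day 30-100 alive, relapse-free and otherwise eligible under sections 4.1 and 4.2 as far as charts show.
2. **Time zero.** Keep transplant as the time scale. Because the comparison concerns patients who receive blinatumomab, enter trial patients into the risk set at first dose; if entry is at enrolment, include everyone enrolled, dosed or not. Enter comparators on the date they first meet all criteria, including any qualifying post-transplant MRD result. A common landmark is acceptable only if group membership is fixed by it.
3. **Adjustment.** Adjust or stratify both groups, not just the cohort, for remission status at transplant and MRD status, with few strata.
4. **Reporting.** Give the hazard ratio with its confidence interval as exploratory. If the CR1 cohort is kept, show it as a descriptive benchmark without a test.

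The cost is protocol wording, a different chart selection and more chart review to date eligibility. There will be fewer comparators and low precision: with all patients CR2-like and left truncation at 12 months, power is about 10-11% for a true hazard ratio of 0.70 and 20-24% for 0.54. The comparison also remains non-randomised, so the amendment removes avoidable bias without establishing a drug effect.

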## 2.0 Background

2.1 Risk for relapse following HCT

Allogeneic HCT is a curative approach for a select group of patients with ALL. Overall survival (OS) ranges from 30%-60%

depending on the patients disease stage and risk profile at time of transplant (1,2).

Increasingly, minimal residual

disease (MRD), both before and after HCT, is becoming an important predictor for relapse (3). In a series of 149 ALL patients transplanted in remission at MD Anderson Cancer Center, patients with MRD, measured by multiparameter flow cytometric immunophenotyping (FCI) with a sensitivity of 0.01%, present at time of HCT had a shorter PFS compared to patients who were MRD negative, 28% vs. 47%,  $p=.08$  (4). Furthermore, among 135 patients who had MRD measured following HCT, 20 became positive for MRD, and 18 of these patients developed

[figure not shown]
[figure not shown]

Figure 1. With a median follow-up of 13 months, 2-year DFS rates are 61%, 40% and 33% for patients in CR1, CR2, and more advanced disease respectively.

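### Section 8.3.1 splits only the comparison cohort by MRD status; the treated group stays pooled under an unstratified log-rank test, so the comparison does not control for MRD

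*Combined protocol and SAP*

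**What the plan says.** Section 8.3.1 defines the comparator: "A contemporary cohort of patients with ALL being transplanted in first complete remission will be identified prospectively". PFS and OS are estimated by Kaplan-Meier, and "differences between the patients receiving blinatumomab and the contemporary cohort will be determined using the log-rank test". The closing sentence of the section is "Patient outcomes in the contemporary cohort will be stratified by MRD status". No sentence classifies the treated patients by MRD, and no stratified test or regression model is given. No time point for MRD is stated. Section 8.3.2 only counts treated patients who are MRD-negative at the end of the study.

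The matching objective is 1.2.1: "To evaluate the progression-free survival (PFS) rate at 1-year for patients with ALL compared to contemporary patient cohort". OS comes under 1.2.2 as a further efficacy endpoint, without a comparator.

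The treated group can be mixed. Section 4.1 lists four alternative disease routes into the study, one of which is "positive minimal residual disease defined by positive flow >0.01% before or after transplant". A patient may instead qualify through remission beyond the first, primary induction failure, or high-risk cytogenetic or molecular features, whatever the MRD result.

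Section 2.1 treats MRD as an important predictor of relapse. In a series of 149 patients transplanted in remission, it reports PFS of 28% with MRD at transplant and 47% without, p=.08.

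**The concern.** A prognostic factor is controlled only if like is compared with like. Splitting the cohort by MRD and leaving the treated group pooled sets a mixed group beside a wholly MRD-positive curve and a wholly MRD-negative curve. If MRD is prognostic, the mixed group tends to lie between them whether or not the drug works. It looks better than one and worse than the other.

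The test that the section does write, treated patients against the undivided cohort, avoids that problem only if both groups happen to have the same MRD mix. Nothing in the plan secures this, since MRD positivity is an entry route on the treated side and the cohort is not selected on it.

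At stake is the reading of the trial's only comparative efficacy analysis. Feasibility is primary and is judged by the stopping rules, so no go/no-go decision depends on this comparison.

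**Working it through.** The documents give no sample size, power or alpha for this comparison, so there is no planned figure to reproduce.

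**Inputs from the documents.** PFS 28% (MRD-positive) and 47% (MRD-negative), section 2.1. At most 30 treated patients, Table 5.

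**Assumptions.** Two-sided 5%; a cohort of 100; MRD-positive shares as listed; exponential event times with 28% and 47% read as 2-year PFS; no drug effect.

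**Step 1: implied MRD effect.** Under proportional hazards, HR = ln(S₁)/ln(S₂). ln(0.28)/ln(0.47) = (−1.273)/(−0.755) = 1.69.

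**Step 2: half-positive treated group, no drug effect.** Expected PFS = 0.5 × 28% + 0.5 × 47% = 37.5%, and ln(0.375) = −0.981.
- Against the MRD-positive part: 0.981/1.273 = 0.77, an apparent benefit.
- Against the MRD-negative part: 0.981/0.755 = 1.30, an apparent harm.

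A mixture is not exactly proportional, so these are approximate.

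**Step 3: whole cohort, unequal mix.** With 70% MRD-positive among treated patients and 30% in the cohort:
- treated: 0.7 × 28% + 0.3 × 47% = 33.7%
- cohort: 0.3 × 28% + 0.7 × 47% = 41.3%
- HR = ln(0.337)/ln(0.413) = 1.088/0.884 = 1.23 against the drug.

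**Step 4: rejection rates for PFS in simulated null trials** (4,000 per row, 30 treated, cohort of 100):

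| MRD-positive, treated / cohort | Whole cohort, unstratified: false benefit + false harm | False benefit vs MRD-positive part | False harm vs MRD-negative part | Log-rank stratified in both groups |
|---|---|---|---|---|
| 25% / 30% | 2.7 + 2.6 = 5.3% | 22.4% | 7.6% | 5.3% |
| 50% / 30% | 0.7 + 7.5 = 8.2% | 12.2% | 17.0% | 5.3% |
| 75% / 30% | 0.1 + 16.9 = 17.0% | 6.1% | 32.3% | 5.2% |
| 50% / 50% | 1.9 + 2.9 = 4.8% | 12.9% | 15.1% | 5.0% |
| 0% / 50% | 14.0 + 0.3 = 14.3% | 41.9% | 2.6% | 5.1% |

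Each one-directional rate should be 2.5%. A separate run at 70% / 30% gave 14.5% rejection against the whole cohort. At 30% / 30% it gave 21% false benefit against the MRD-positive part. The test stratified in both groups stayed at 5-6%. Other follow-up patterns move these figures by a point or two.

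Three results follow. The whole-cohort test is close to nominal when the mixes agree and drifts in either direction when they do not. A single-stratum reference misleads even when the mixes agree. Stratifying both groups restores the nominal rate for this factor. As a control, with no MRD effect (50% / 30%) the whole-cohort test rejects in 2.0 + 2.9 = 4.9%.

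**The case against.** The strongest reply is that the log-rank sentence already names the contrast, blinatumomab patients against the undivided cohort, and that objective 1.2.1 puts PFS first. The MRD sentence mentions no test and may promise no more than descriptive curves. That stands. A reader might infer that the plan sets up six competing tests (three references for each of PFS and OS) with none chosen, and might quote a 34% chance of some nominally significant result. The documents do not support this: that figure requires tests the plan never lists, run and then selectively reported. The missing alpha, ordering and exploratory label are absent detail.

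A reader might also infer that the trial could reach significant conclusions in opposite directions. In the simulations both single-stratum results were significant and opposite in at most 0.2% of null trials. What differs is the direction of the estimates, or significance against one reference and not the other.

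The size is also open to challenge. The 28% and 47% differ with p=.08, have no time point, and come from patients transplanted in remission generally, not from first remission alone. The rates above are therefore illustrative. The direction of the bias needs only that MRD be prognostic, which is the protocol's own premise.

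Finally, pre-transplant MRD is not shown to be recorded for every treated patient. Eligibility accepts MRD before or after transplant, and the Table 3 marrow falls after transplant. This limits the choice of time point and is carried into the fix.

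**Conclusion.** The point holds as a modest and cheap improvement to a secondary analysis. As written, neither the whole-cohort test nor a single-stratum reference controls for MRD. On the Background's figures, an undrugged half-positive group has a hazard ratio of about 0.77 or 1.30 depending on the stratum beside it. The whole-cohort test rejects in about 8% to 17% of null trials when 50% to 75% of treated patients and 30% of the cohort are MRD-positive, and at about 5% when the mixes agree. These sizes rest on the stated assumptions and on an MRD effect that the source series estimates imprecisely.

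It would go too far to infer that MRD stratification makes the comparison sound. The cohort is limited to first remission while eligibility admits later remissions. The Background's 2-year DFS of 61% and 40% in first and second remission implies a hazard ratio of ln(0.40)/ln(0.61) = 1.85 against such patients with no drug effect. That bias is separate and would remain.

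**What to change.** Replace the last sentence of section 8.3.1 with:

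> The comparison of PFS (and, as a supporting analysis, OS) between blinatumomab patients and the contemporary cohort will use a log-rank test stratified by MRD status (positive/negative) in both groups, with MRD assessed at the same stated time point relative to transplant in both. The 1-year PFS estimates of objective 1.2.1 will be given with 95% confidence intervals by group and MRD stratum. The pooled blinatumomab group will not be compared with a single MRD stratum of the cohort.

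The sponsor should choose a time point at which MRD is available for all patients in both groups. A time point after transplant falls after the start of the PFS clock, so that choice would need its own provision. The result should be labelled exploratory because of the first-remission comparator.

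The cost is a few sentences and a check on MRD records. The statistical price is small strata, with at most 30 treated patients, and slightly less precision. If one stratum has no treated patients, it contributes nothing to the test.
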